### **13.3 Data Analysis**

Primary endpoint analyses will be conducted after all enrolled participants have completed Week 24. A final analysis of all data will be conducted after Week 52 is complete. Safety data and efficacy analyses will be updated at Week 36.

#### **13.3.1 Analysis of Baseline and Demographic Data**

Demographics and baseline characteristics will be summarized by treatment group for all randomized subjects. Data will be pooled for all centers for baseline data analysis. The F test of the Type III treatment factor from a one-way ANOVA model including only the treatment factor will be used to analyze numeric variables. The Fisher's Exact test will be used to analyze categorical data. Overall comparisons between treatment groups will be performed. Nominal comparisons between treatment groups will be performed for baseline data to assess treatment group balance across the various baseline characteristics. These comparisons will be considered non-inferential; nominal p-values will be reported with no statistical conclusion and no adjustment for multiple tests will be made.

#### **13.3.2 Safety Analysis**

All randomized subjects who received treatment will be included in a final safety data analysis which will include all data through Week 52 as the as-treated cohorts. In addition to descriptive summaries of all AEs by treatment group, Fisher's Exact test will be used to compare the incidence of the most frequent AEs or SAEs between treatment groups. The MedDRA system will be used to map each AE verbatim term to the system organ class (SOC) and preferred term (PT) for summary purposes. AE data, including the AE verbatim term and the associated AE preferred term, will be provided in the subject data listings. Note that once enrollment of TOL-3021 studies is expanded to adolescent participants aged 12.0 to <18 years of age, data from adolescent participants will be summarized and presented separately from data on adult participants in all subsequent DSMB review meetings.

Adverse event incidence summaries, including incidence rates of SAEs and TEAEs, will be generated on a monthly basis on live data. These will be reviewed in real time by the Sponsor and Emmes, with the treatment groups labeled as "A" and "B." An excessive rate in any specific AE or SAE may result in referral to the DSMB for review. The study statistician will maintain these reports and all resulting correspondence. The code may be requested to be broken by the DSMB after receiving Sponsor approval.

Other safety data, such as laboratory data, physical examination data, and abnormal findings, will be tabulated and/or graphically displayed. Concomitant medications used during the study will be summarized. Medications discontinued prior to the randomization date will be excluded from the summary.

Safety data collected after Week 52 will be analyzed separately from safety data collected during the controlled trial period.

After 6 subjects aged 14-<18 years of age have been enrolled with the last subject having a minimum of 2 injections with at least 1 week follow-up after the 2nd injection. Safety data from these initial subjects will be evaluated before opening the study to subjects 12 and older.

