### **2.2 Safety Objective**

To evaluate the safety of TOL-3021 administered as weekly intramuscular (IM) injections over 52 weeks in patients with Type 1 Diabetes Mellitus (T1D).

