**Figure 3. Study Schematic**

## 4 OUTCOMES

### 4.1 Safety Outcomes

The following will be tracked and monitored through the course of the study

- Clinical laboratory tests (hematology, chemistry, urinalysis);
- Urine pregnancy test (UPT) for women of childbearing potential (WOCBP);
- Concomitant medications;
- Collection of adverse events (AEs);
- Vital signs;
- Injection site reactions;
- Severe hypoglycemia or hyperglycemia events monitored by CGM;
- Events of special interest:
  - Systemic or hypersensitivity reactions associated with injection, which consist of fever, chills, headache, nausea, vomiting, and/or other signs and symptoms, such as anaphylaxis, wheezing dyspnea, urticaria, and hypotension

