### **5.3.2 Trial Stopping Rules**

Study enrollment or study drug administration may be suspended if certain events occur during the trial. The chairman of the DSMB will be notified that a review of safety data

may be required to determine procedures that need to be implemented if any of the following occur:

- Any death deemed to be related to study therapy
- More than one hospital admission of the same event based on MedDRA preferred term for an unexpected treatment-related SAE
- Three of the first 10 subjects, or 30% thereafter, require discontinuation of study medication for the same or similar serious adverse event based on MedDRA preferred term or at the discretion of Sponsor and/or Medical Monitor

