## 13 STATISTICAL CONSIDERATIONS

### 13.1 Sample Size/Power Considerations

Up to 99 subjects will be randomized 2:1 to active and placebo treatments. For analytic purposes all subjects 12- <41 years of age will be considered cohort A. A minimum of 18 and a maximum of 24 subjects aged 12 and <18 years of age will comprise Cohort B. Adult subjects aged 18- <41 will comprise cohort C. The proposed study is powered to detect approximately an overall 13% difference between treatment and placebo groups in a repeated measures mixed model analysis of the mean plasma C-peptide AUC over 4-hour MMTT at Week 12, 16, and 24 weeks as compared to the subject's baseline. A total of 90 subjects will provide 90% power to detect this difference at a significance level (alpha) of 0.05; a total of up to 99 subjects will be randomized to allow for an anticipated drop-out rate of approximately 10%. Insulin secretion as reflected by C-peptide declines more rapidly in younger patients, including adolescents. TOL-3021 is expected to have equal or even greater effect in the adolescent population compared to the effect observed in the phase 2a study of adult subjects only. An effect was detectable in the 17 adults who received 12 weeks of 1.0 mg treatment in that study. Based on assumption of an overall difference between treatment and placebo groups of 20%, then a minimum of 18 adolescents aged 12- <18 (Approximately 12 active and 6 placebo) would provide 80% power to detect a difference at a significance level (alpha) of 0.05, providing an initial estimate of efficacy and a description of safety in this population Cohort B (ages 12- <18) and cohort C (ages 18- <41) and will be analyzed separately as well as combined.

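### The only formal safety comparison is a Fisher test on the most frequent events; risk differences with 95% intervals for named safety events would serve the safety objective better

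*Protocol*

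**What the plan says.** The synopsis calls safety a primary objective, and section 2.2 states it: "To evaluate the safety of TOL-3021 administered as weekly intramuscular (IM) injections over 52 weeks". No safety hypothesis, margin or detectable difference is attached. For adolescents, section 13.1 promises only a trial "providing an initial estimate of efficacy and a description of safety in this population".

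Section 13.3.2 sets out the safety analysis through Week 52:

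- It opens with "In addition to descriptive summaries of all AEs by treatment group" and then adds the formal comparison, Fisher's "Exact test will be used to compare the incidence of the most frequent AEs or SAEs between treatment groups". No alpha, sidedness, effect measure or frequency cut-off is given.
- Laboratory and examination findings are tabulated or graphed.
- During the trial, "Adverse event incidence summaries, including incidence rates of SAEs and TEAEs, will be generated on a monthly basis on live data", with the arms coded, and "An excessive rate in any specific AE or SAE may result in referral to the DSMB for review".

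Section 5.3.2 adds event-based review triggers, for example "Three of the first 10 subjects, or 30% thereafter, require discontinuation of study medication for the same or similar serious adverse event". Section 4.1 names one class of events of special interest: "Systemic or hypersensitivity reactions associated with injection".

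**The concern.** A Fisher p-value answers whether chance alone could explain an imbalance. The safety objective needs something else: how large an excess risk was seen, and how large an excess the data still allow. In a trial of 99 subjects the two can diverge widely, because a clearly non-significant p-value can sit beside an interval reaching well past 20 percentage points.

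The choice of events adds to this. Testing only the most frequent ones means that systemic and hypersensitivity reactions, which the protocol singles out, are formally compared only if they happen to be common.

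Section 13.3.1 labels the baseline p-values nominal and says no conclusion will be drawn from them. Section 13.3.2 has no such caution for safety p-values, where a wrong reading would cost more.

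**Working it through.** **Inputs**

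- Arm sizes: section 13.1 gives 90 evaluable subjects plus about 10%, and 90 × 1.10 = 99 reproduces the planned total. At 2:1 that is 66 active and 33 placebo. The protocol states no power for any safety comparison, so there is no safety figure to reproduce.
- Adolescents: section 13.1, minimum 18, about 12 active and 6 placebo.
- Phase 2a rates: section 1.1, Table 2, 1.0 mg v placebo. Possibly related TEAEs 6/18 = 33.3% v 6/26 = 23.1%; Grade 3 or higher 4/18 = 22.2% v 4/26 = 15.4%.
- Assumed: two-sided 0.05, unadjusted. All rates other than those from phase 2a are illustrative.

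**Step 1. Power of the Fisher test.** Full enumeration, with a and b the active and placebo counts:

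Power = Σₐ Σ_b Bin(a; 66, p₁) × Bin(b; 33, p₀) × 1{Fisher p ≤ 0.05 and a/66 > b/33}

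| Active v placebo | Power at 66 v 33 |
|---|---|
| 22.2% v 15.4% (phase 2a, Grade 3 or higher) | 9% |
| 33.3% v 23.1% (phase 2a, possibly related) | 15% |
| 20% v 10% | 19% |
| 5% v 0% | 2% |
| 10% v 0% | 34% |
| 20% v 5% | 47% |
| 30% v 10% | 60% |
| 20% v 0% | 97% |

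Power is slightly lower at 60 v 30. The same sum at 12 v 6 gives 5% for 40% v 20%.

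**Step 2. Smallest significant count with no placebo events**

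- 66 v 33: 7/66 v 0/33 gives p = 0.092; 8/66 (12.1%) v 0/33 gives p = 0.049.
- 12 v 6: 6/12 v 0/6 gives p = 0.054; 7/12 (58%) v 0/6 gives p = 0.038.

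**Step 3. What an interval would add.** Take whole-number counts near the phase 2a possibly related rates: 22/66 = 33.3% and 8/33 = 24.2%. Fisher gives p = 0.49. For the Newcombe interval, the Wilson limits are 23.2% to 45.3% (active) and 12.8% to 41.0% (placebo), and the difference is 9.1 points.

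- Lower: 9.1 − √[(33.3 − 23.2)² + (41.0 − 24.2)²] = −10.5 points
- Upper: 9.1 + √[(45.3 − 33.3)² + (24.2 − 12.8)²] = +25.7 points

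Similarly, 7/66 v 0/33 (p = 0.092) has an interval of −1.1 to +20.3 points, and 4/66 v 1/33 (p = 0.66) one of −9.8 to +11.9 points.

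**Step 4. Upper limit when no active-arm events occur.** The exact one-sided 95% limit is 1 − 0.05^(1/n):

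- n = 66: 4.4%
- n = 12: 22.1%

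**The case against.** The strongest reply is that nothing in section 13.3.2 is false. A Fisher test beside by-arm counts is conventional at this size, and intervals, event lists and cut-offs usually belong in the SAP, which is not at hand. That stands in part: the absence of an interval is not in itself an error. But the protocol does fix a method here, and a better one is available at almost no cost.

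Several stronger readings are tempting, and the protocol does not support them:

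- *The p-value is the only comparative output.* It is the only formal test. All AEs are summarised by arm, incidence is reviewed monthly by coded arm, and neither DSMB referral nor the section 5.3.2 triggers depend on a p-value.
- *Events of special interest are not compared between arms.* They are AEs, so they appear in the by-arm summaries. What they may lack is a formal comparison.
- *The test misses most relevant harms.* It has low power for moderate excesses, but 20% v 0% has 97% power.
- *The plan treats non-significance as proof of safety.* It never says so.
- *A Fisher result opened the trial to adolescents.* That step rested on DSMB and regulatory review of Week 12 data, and the further step to age 12 rests on safety data from the first six subjects aged 14 to under 18. No Fisher test is named at either step.

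It is also fair to say that insensitivity to rare harms comes from the sample size. An interval displays that limit and does not remove it.

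**Conclusion.** The point holds as an improvement to a stated method, not as a gap in safety monitoring. Section 13.3.2 makes a p-value on frequent events its only formal comparison. At the planned size that test would miss the phase 2a imbalance in possibly related events about 85% of the time (100% − 15%). A non-significant result can coexist with an excess of about 12 to 26 points in the worked examples. No output named in the protocol puts a figure on that remaining uncertainty, and the named events of special interest are formally compared only if common.

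The power figures assume a two-sided 0.05 test and full arms of 66 and 33. The phase 2a rates come from 18 and 26 subjects given 12 weekly doses, so they illustrate scale and do not predict rates over 52 weeks. The adolescent figures apply if the same test is run separately in Cohort B.

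**What to change.** In section 13.3.2, or in the SAP with a pointer from it:

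1. Report the risk difference, TOL-3021 minus placebo, with a two-sided 95% score or exact interval for SAEs, events of special interest, injection-site reactions, severe hypoglycemia and the most frequent AEs.
2. Do this overall, and descriptively for Cohorts B and C.
3. Where an event does not occur on active treatment, give the exact upper limit on the active-arm rate.
4. Keep any Fisher p-values as nominal and non-inferential, in line with section 13.3.1 for baseline data.

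No new data are needed. The cost is a few more table columns and openly wide intervals, most of all in Cohort B.

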### **13.3.3 Efficacy Analysis**

The analysis of the primary outcome, MMTT-stimulated 4-hour mean C-peptide AUC at multiple time points will test the null hypothesis of “no treatment group difference” versus the two-sided alternative using the intent-to-treat (ITT) cohorts. The treatment-group main effect hypothesis test will be derived from a repeated measures mixed model of the log-transformed 4-hour C-peptide AUC response at 12, 16 and 24 weeks, adjusted for the baseline C-peptide AUC, age group and T1D-duration group. Missing data for this analysis will be imputed for each subject based on any available data. To be imputed, a data point must have data for the visit before and the visit after the missing data point, and the slope between the two non-missing visits will be used to impute the missing data. A secondary method using a mixed model for repeated measures (MMRM) approach will also be utilized for the primary and secondary endpoints that cannot be imputed using the approach above. Additional details for this approach will be provided in the statistical analysis plan.

### **13.3.4 Pharmacokinetic / Pharmacodynamic Analysis**

No pharmacokinetic or pharmacodynamic analyses will be conducted.

### **13.3.5 Immunoprofiling**

Quantum dot (Q-dot) responses within the qualifying subpopulation (HLA class I types for which multimers are available) will be conducted to confirm induction of specific autoantigen tolerance. Analysis of immunological endpoints will be conducted on the intent-to-treat (ITT) and per protocol populations. Pre-treatment and post-treatment values for T cell responses and T1D antibodies will be summarized over time, as well as the frequency of T cell immune responses and T1D antibodies and the strength of the immune responses.

Q-dot (quantum dot) flow cytometry will be used to measure CD8+ T cell responses to various epitopes from individuals who have HLA-A2, HLA-A3, or HLA-B7 haplotypes.

The frequency of CD8+ T cells responding to proinsulin GAD, IA2, PPI leader sequence, islet amyloid polypeptide (IAPP), and IGRP before and after the 52-week treatment period will be measured and compared to C-peptide response.

It is known that immune responses to injected insulin may develop after initiation of insulin therapy. Consequently, antigen presentation resulting from insulin therapy may act as to confound immune responses induced by TOL-3021. This interaction will be accessed by measuring CD8+ T cell responses to an insulin epitope (insulin B10-18) contained within injected human insulin and to two other epitopes unique to TOL-3021. CD8+ responses to viral epitopes on EBV, CMV, and measles will also be measured with Q-dot flow cytometry.

Serum insulin, glutamic acid decarboxylase, IA-2 and ZnT8 autoantibodies, and insulin autoantibody affinity will be measured before, during, and after the 52-week treatment period. Insulin autoantibody isotypes (IgA and IgM) and IgG subclasses for subjects will also be evaluated.

## **14 ESTIMATED DURATION OF THE STUDY**

This study has an estimated duration of up to 4 weeks for screening, 52 weeks of treatment and two years of follow-up after randomization per subject. This study has an estimated overall duration of approximately 42 months, including recruitment, screening, a 52-week treatment, and a 2-year safety follow-up.

## **15 ADMINISTRATIVE PROCEDURES AND ETHICAL CONSIDERATIONS**

### **15.1 Medical Care**

Subjects will receive routine care throughout the trial. The study is designed to monitor the status of the subject's T1D throughout the study by collecting information on daily insulin use, glucose levels, episodes of hypoglycemia, local and systemic reactions to study drug, AEs, and use of concomitant medications. Subjects will be provided with information for management of their diabetes at the screening visit and throughout the study. Subjects will have clinic visits weekly during the 4 weeks after randomization and then approximately monthly until study completion.

### **15.2 Subject Information and Informed Consent**

The informed consent process (and assent process for 12-<18 years of age) is initiated prior to the individual's agreeing to participate in the study and continues throughout the individual's study participation. The consent and assent forms will be submitted with the protocol for review and approval by the IRB and sponsor prior to use. The subject and

subject's guardian where applicable, will be asked to read and review the document. The PI or designee will explain the research study to the subject and answer any questions that may arise. A verbal explanation will be provided in terms suited to the subject's comprehension of the purposes, procedures, and potential risks of the study and of their rights as research subjects. Subjects (and parent/legal guardian where applicable) will have the opportunity to carefully review the written consent form and ask questions prior to signing. The subjects will have the opportunity to discuss the study with their family or surrogates or think about it prior to agreeing to participate. The subject (or legally accepted surrogate) will sign the informed consent/assent document prior to any procedures being done specifically for the study. Potential subjects must be informed that participation is voluntary and that they may withdraw from the study at any time, without prejudice. A copy of the informed consent and assent document, where applicable will be given to the subject for their records. The informed consent process will be documented in the source document, and the form signed, before the subject undergoes any study-specific procedures. The rights and welfare of the subjects will be protected by emphasizing to them that the quality of their medical care will not be adversely affected if they decline to participate in this study.

### **15.3 Ethics Committee Review**

The protocol, informed consent and assent form and any subject information sheet must be approved in writing by the appropriate Department of Health and Human Services (HHS)-registered IRB before the study can be initiated at a site. A copy of the IRB approval must be sent to the Sponsor (or designee) along with a list of the IRB members and their occupations/affiliations. IRB approval is also required for any advertising or other material used for subject recruitment, and for instructions provided to the subject. If the protocol is amended, the PI must sign the revised protocol and submit the amendment to the IRB for review and approval prior to implementation of the changes specified in the amendment. The PI must report promptly to the IRB all changes in the research activity and all unanticipated problems involving risk to human subjects or others, including all serious adverse events that have resulted in an expedited safety report to the FDA. No drug will be shipped to a site until IRB approval has been granted and the Sponsor or designee has been notified of this in writing.

The PI is responsible for obtaining continued review of the clinical study at intervals not to exceed one year or otherwise specified by the IRB. The PI must provide the Sponsor (or designee) with written documentation of the continued review.

## **15.4 Standards**

### **15.4.1 Ethics and Responsibility**

This study will be conducted in compliance with the protocol and according to US and international standards of Good Clinical Practice (FDA regulations 21 CFR 312 for IND studies and ICH guidance E6) for all studies. PIs must submit all essential regulatory documentation, as required by local and national regulations (including IRB approval of the protocol and informed consent form) to the Sponsor or its designee before investigational product will be shipped to the study site.

### **15.4.2 Monitoring, Compliance, Quality**

All aspects of the study will be monitored by the authorized representatives of the Sponsor according to GCP and Standard Operating Procedures (SOPs) for compliance with applicable government regulations, (i.e., Informed Consent Regulations and IRB regulations).

The PI must conduct the protocol in compliance with applicable GCP regulations and guidelines, applicable informed consent regulations, and the Declaration of Helsinki (APPENDIX 3). Every attempt must be made to follow the protocol and to obtain and record all data requested for each subject at the specified times. If data is not recorded per protocol, the reasons must be clearly documented on the source documents or other study records.

Access to all records, both during the trial and after trial completion, should be made available to the Sponsor or its designee at any time for review and audit to ensure the integrity of the data. The PI must notify the Sponsor or its designee immediately if the responsible IRB/IEC has been disqualified by local health authorities or if proceedings leading to disqualification have begun.

Before study initiation, at a site initiation visit or at a meeting with the PI(s), a Sponsor representative will review the protocol and study documents, including eCRFs, with the PI(s) and their staff.

CRA's will perform ongoing site visits to confirm that critical protocol data (i.e., source data) entered into the eCRFs by authorized site personnel are accurate, complete, and verifiable from source documents. In addition, the CRA will review the site's adherence to the protocol and to GCP, as well as the progress of enrollment. The CRA will ensure that consent is being sought and obtained in compliance with applicable regulations, and that the investigational product is being stored, dispensed, and accounted for according to

specifications. The PI or designee must promptly complete the eCRFs after the subject's visit.

Source documents are where subject data are recorded and documented for the first time. They include, but are not limited to, hospital records, clinical and office charts, laboratory results, memoranda, evaluation checklists, recorded data from automated instruments, copies of transcriptions that are certified after verification as being accurate and complete, photographic negatives, magnetic media, and medico-technical departments involved in the clinical trial.

To facilitate monitoring, the PI(s) and institution(s) must provide the Sponsor direct access to applicable source documents and reports for trial-related monitoring, Sponsor audits, and IRB review. The site must also allow inspection by applicable regulatory authorities. The PI and key trial personnel must be available to assist the monitor during these visits.

When clinical observations are entered directly into the site's computerized medical record system (i.e., in lieu of original hardcopy records), the electronic record can serve as the source document if the system has been validated in accordance with FDA requirements pertaining to computerized systems used in clinical research. An acceptable computerized data collection system (for clinical research purposes) would be one that (1) allows data entry only by authorized individuals, (2) prevents the deletion or alteration of previously entered data and provides an audit trail for such data changes (e.g., modifications of file), (3) protects the database from tampering, and (4) ensures data preservation.

If a site's computerized medical record system is not adequately validated for the purposes of clinical research (as opposed to general clinical practice), applicable hardcopy source documents must be maintained to ensure that critical protocol data entered into the eCRFs can be verified.

Subjects (or their legal representatives) must also be allowed access to their medical records. Subjects will be informed of the importance of increased record access and granted permission by signature on the informed consent document prior to Screening. No information in these records about the identity of the subjects will leave the study center. Monitoring standards require full verification for the presence of informed consent, adherence to the inclusion/exclusion criteria, documentation of SAEs, and the recording of primary efficacy and safety variables. Additional checks of the consistency of the source data with the CRFs will be performed according to the study-specific monitoring plan.

Emmes, the CRO monitoring this clinical trial, will follow standard operating procedures for monitoring this study in accordance with GCP recommendations and FDA regulatory requirements. Any site not meeting the minimum requirements to initiate the trial, or that

has administrative, procedural, or data quality deficiencies that require correction in order to comply with or meet regulatory requirements or the protocol, will be notified in writing of the deficiencies and permitted a reasonable opportunity to rectify deficient conditions. After study initiation, the inability of the site to rectify seriously deficient conditions in a timely manner or to maintain compliance with regulatory requirements may be cause for termination of study activities, closure of the investigational site, and notification of that decision to the relevant IRB) or IEC and other regulatory authorities as appropriate.

Participating sites will have an initial monitoring visit, routine interim monitoring visits during the study, and a study close-out visit conducted by experienced CRAs. Additional monitoring visits may be performed for cause or if the volume of information to be reviewed cannot be easily completed in a single visit. All attempts will be made to schedule the study visits in advance so that necessary site staff and appropriate records will be available during the monitoring visit.

Each monitoring visit will utilize a standardized checklist of elements to be reviewed at the site, tailored to the specific requirements of this study. Site monitoring visits will routinely review the participating site staff roster; administrative and financial documents; required regulatory documentation; status of IRB/IEC approvals; changes or actions taken since any previous visit; subject recruitment status, screening, enrollment, and follow-up visit records; documentation of informed consent for each subject; review of adverse events; investigational product storage conditions; outstanding data clarifications, and data elements against source documentation. Site visits will follow the study-specific monitoring plan procedures, and a summary report will be prepared for study records. The CRA will also investigate any questions concerning adherence to regulatory requirements. Any administrative concerns will be clarified and followed. The CRA will maintain contact with the site through frequent direct communications with the study site by e-mail and telephone. The PI and all other site personnel agree to cooperate fully with the monitor and will work in good faith with the CRA to resolve any and all questions raised, and difficulties detected by the CRA.

